### Confirmed best overall response (cBOR)

cBOR according to RECIST 1.1 as adjudicated by IRC will be assessed according to the following rules:

- CR = at least two determinations of CR at least 4 weeks apart and before progression  
Note: It is reasonable to consider CR-NE-CR or CR-PR-CR as CR as long as the second CR is more than 28 days away from the first timepoint.
- PR = at least two determinations of PR at least 4 weeks apart and before progression (and not qualifying for a CR)  
Note: It is reasonable to consider PR-NE-PR or PR-SD-PR as PR as long as the second PR is more than 28 days away from the first timepoint
- SD = at least one SD assessment (or better)  $\geq$  6 weeks after first date of study intervention and before progression (and not qualifying for CR or PR)
- Non-CR/Non-PD= at least one Non-CR/Non-PD assessment  $\geq$  6 weeks after first date of study intervention and before progression with no measurable disease and does not meet criteria of CR

Note: As tumor lesions are evaluated by the IRC, it may happen that the independent reviewer disagrees with the Investigator and does not assess any tumors as “measurable” at screening. However, as per inclusion criteria, measurable disease must be confirmed by IRC at inclusion, so such case is not expected to occur. But in case of Non-CR/Non-PD, the overall response is rated as “non-CR/non-PD” (if no “CR” or “PD” are previously reported) by the IRC. Non-CR/Non-PD is specific to IRC assessment (it does not apply for Investigator assessment)

- PD = progression  $\leq$  16 weeks after first date of study intervention (and not qualifying for CR, PR or SD)
- ND = at least one ND assessment

Note: Overall response is rated as “No Disease” (ND) when the IRC is not able to identify any disease at baseline (target or non-target lesions). However, as per inclusion criteria, measurable disease must be confirmed by IRC at inclusion, so such case is not expected to occur. ND is specific to IRC assessment (it does not apply for Investigator assessment)

- NE = all assessments are NE or participant has a missing (or not evaluable) baseline tumor assessment and/or no (or not evaluable) tumor assessments on-treatment, or participant does not complete any of the following response above

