### Unconfirmed best Overall Response (uBOR)

uBOR according to RECIST 1.1 as adjudicated by IRC will be assessed according to the following rules:

- CR = at least one determination of CR

- PR = at least one determination of PR (and does not meet criteria of CR)
- SD = at least one SD assessment  $\geq$  6 weeks after start date and before progression (and does not meet criteria of CR or PR)
- Non-CR/Non-PD = at least one Non-CR/Non-PD assessment  $\geq$  6 weeks after start date and before progression with no measurable disease (and does not meet criteria of CR)

Note: As tumor lesions are evaluated by the IRC, it may happen that the independent reviewer disagrees with the Investigator and does not assess any tumors as “measurable” at screening. However, as per inclusion criteria, measurable disease must be confirmed by IRC at inclusion, so such case is not expected to occur. But in case of Non-CR/Non-PD, the overall response is rated as “non-CR/non-PD” (if no “CR” or “PD” are previously reported) by the IRC. Non-CR/Non-PD is specific to IRC assessment (it does not apply for Investigator assessment)

- PD = progression  $\leq 16$  weeks after first date of study intervention (and does not meet criteria of CR, PR, SD or Non-CR/Non-PD)
- ND = at least one ND assessment

Note: Overall response is rated as “No Disease” (ND) when the IRC is not able to identify any disease at baseline (target or non-target lesions). However, as per inclusion criteria, measurable disease must be confirmed by IRC at inclusion, so such case is not expected to occur. ND is specific to IRC assessment (it does not apply for Investigator assessment)

- NE = all assessments are NE or participant has a missing (or not evaluable) baseline tumor assessment and/or no (or not evaluable) tumor assessments on-treatment, or participant does not complete any of the following response above

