### **Disease Control Rate (DCR)**

Disease Control Rate (DCR) is defined as the proportion of participants with BOR according to evaluation criteria of CR, PR, or SD out of the total number of participants.

Separate tables will be provided for confirmed and unconfirmed BOR. Each one will provide the number and percentage of participants with cBOR (respectively uBOR) of CR, PR, SD, Non-CR/Non-PD, PD, ND and NE as well as the ORR and the DCR. The ORR and DCR will be provided with a two-sided 95% CI using the Clopper-Pearson method (exact CI for a binomial

proportion as computed by default by the FREQ procedure using the EXACT option). Exact binomial test (1 sample) against the null hypothesis for the ORR will be calculated for confirmed BOR to determine whether the null hypothesis of an ORR  $\leq 10\%$  can be rejected.

The individual percentage of change in the sum of diameter since baseline will be displayed over time on a spider plot, together with the first occurrence of new lesion and the participant off treatment. The change in the sum of diameters between baseline and the best post-baseline assessment (i.e. minimum change since baseline) will be displayed on a waterfall graph. Note the sum of diameters includes all target lesions (longest diameter for non-nodal lesions and short axis for nodal target lesions)

The best percent change in sum of target lesion diameters will also be presented in a waterfall plot with confirmed BOR per IRC and investigator, PD-L1 in tumor cells and immune cells, **CCI**, **CCI** and **CCI** status.

For spider plots and waterfall plots, the percent change from baseline in the sum of diameters will be displayed for valid timepoint assessments, only. For the purpose of this analysis, a valid timepoint assessment is defined as a complete assessment of all target lesions reported at baseline. Further, split and coalesced lesions have to be taken into account appropriately to determine if a timepoint assessment is valid to derive the percent change from baseline in sum of diameters. All sum of diameters should be used, including the ones beyond first PD (for waterfall plot, the best post-baseline sum of diameters will be used even if occurring beyond PD). For waterfall plot, the percent change from baseline to 8-weeks assessment, as well as the percent change from baseline to the best post-baseline sum of diameters will be displayed for each participant.

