## 14.4

## Progression-Free Survival (Secondary Endpoint)

Analysis (Analysis Population)	Derivation	Statistical Analysis Methods	Missing data handling
Secondary endpoint: Progression-Free Survival (PFS)			
Secondary analysis (ITT)	Time from first administration of study treatment until the first documentation of progression of disease (PD) or death due to any cause, whichever occur first, per RECIST 1.1 as measured by the IRC.	Kaplan-Meier estimates (product-limit estimates) will be presented together with a summary of associated statistics (median time, 3-, 6-, 9-, 12-, 24-month rate estimates) including the corresponding two-sided 95% confidence intervals. The confidence intervals for the median will be calculated according to Brookmeyer and Crowley (1982) and confidence intervals for the survival function estimates at above defined timepoints will be derived using the log-log transformation according to Kalbfleisch and Prentice (2011) (conftype=loglog default option in SAS Proc LIFETEST). The estimate of the standard error will be computed using Greenwood's formula.	
PFS will be censored at the date of last progression-free tumor assessment or date of first study treatment, whatever is later.
 
Censoring rules (details provided in body text):
 

- No event (PD or death)

- No baseline and/or post-baseline assessment

- Start of new anticancer treatment

- Event after two or more subsequent missing response assessments

Sensitivity analysis 1 (ITT)			
PFS will be censored at the date of last tumor assessment with outcome CR, PR or SD or date of first study treatment, whatever is later.
 
Censoring rules (details provided in body text):
 

- No event (PD or death)

- No baseline and/or post-baseline assessment

Sensitivity analysis 2 (ITT)	Time from first administration of study treatment until the first documentation of progression of disease (PD) or death due to any cause, whichever occur first, per RECIST 1.1 as measured by the Investigator.	PFS will be censored at the date of last tumor assessment with outcome CR, PR or SD or date of first study treatment, whatever is later.

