Sensitivity Analysis 1: PFS counting all events (PD and death) regardless of the start of a new anticancer therapy and ignoring the number of missing evaluable tumor assessments before progression or death

Sensitivity Analysis 2: PFS as assessed by the Investigator

\* with outcome CR, PR or SD. If no adequate tumor assessment, censored at date of first administration of study treatment

a No assessments in 112 days during the first 12 months of follow-up or 168 days after the first 12 months of follow-up

PFS according to RECIST 1.1 as measured by the IRC will be described (secondary endpoints).

The analysis of PFS will be performed with a Kaplan-Meier method (product-limit estimates) and a summary of associated statistics will be presented including corresponding two-sided 95% CIs. The CIs for the median will be calculated according to Brookmeyer and Crowley (1982) and CIs for the survival function estimates will be derived using the log-log transformation according to Kalbfleisch and Prentice (1980) (CONFTYPE=loglog default option in SAS PROC LIFETEST). The estimate of standard error will be computed using Greenwood's formula.

Frequency (number and percentage) of participants with and without event and within each event type (PD or death) will be presented as well as the PFS median, min and max. Number of participants at risk, failed and PFS rates with their CI at 6, 12 and 24 months will also be provided. Censoring reasons will also be described. Censoring reasons are as follows:

- Administrative censoring (ongoing in the study without an event)
- No baseline assessment
- No evaluable post-baseline assessment
- Start of new anticancer therapy
- Event after 2 or more missing or non-evaluable post-baseline assessments
- Withdrawal of consent
- Lost to follow-up

Lost to follow-up will include the following participants:

- Lost to follow-up status is collected on the eCRF treatment termination page or eCRF study termination page prior to the analysis cut-off
- Participants with the last alive date > 14 weeks prior to the analysis cut-off date (duration of 14 weeks is based on the assessment schedule of every 3 months for survival follow-up interval + 2-weeks window)

PFS will also be presented graphically with Kaplan-Meier figures.

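### SAP 14.4 gives conflicting PFS censoring dates for a participant the IRC rates Non-CR/Non-PD, and the confirmed-BOR PD rule lets that rating overlap with PD

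*SAP*

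**What the plan says.** **The rating.** SAP 14.1 defines Non-CR/Non-PD, for IRC reads only, as no measurable disease, neither complete response nor progression, at 6 weeks or later. It explains that "it may happen that the independent reviewer disagrees with the Investigator and does not assess any tumors as" measurable. It adds that this is not expected, because the IRC must confirm measurable disease at inclusion (Protocol 5.1, criterion 5). The category is kept separate from NE and has its own row in the response tables.

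**PFS censoring, SAP 14.4.**
- Summary table, primary row: "PFS will be censored at the date of last progression-free tumor assessment or date of first study treatment, whatever is later".
- Body text: the last tumor assessment is the latest one that is available and evaluable. First dose is used only if there is none.
- Table 5: the primary and both sensitivity columns censor at a starred last tumor assessment. The star means one "with outcome CR, PR or SD. If no adequate tumor assessment, censored at date of first administration of study treatment".
- Summary table, Sensitivity Analysis 1 row: "PFS will be censored at the date of last tumor assessment with outcome CR, PR or SD or date of first study treatment".

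Protocol 9.4.1.2.1 censors at the last adequate assessment and lists no qualifying outcomes. It uses first dose only when baseline or post-baseline assessments are missing. SAP 7 states that nothing was changed from the protocol.

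**Best overall response, SAP 14.1.** The unconfirmed PD category applies if progression occurs by 16 weeks "and does not meet criteria of CR, PR, SD or Non-CR/Non-PD". The confirmed PD category has the same time limit but excludes only CR, PR and SD.

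**The concern.** A Non-CR/Non-PD scan shows that the participant has not progressed. Under the footnote it does not count, so a participant with nothing but such scans has no adequate assessment and contributes no progression-free time. Under the primary row and the body text, the same participant contributes time up to the last scan. Both rules are written for the same analysis, so the programmer must choose, and in an open-label single-arm trial that choice could be made with the data in view.

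Sensitivity Analysis 1 is meant to vary only two things: the handling of new anticancer therapy and of missed scans. If the primary analysis follows the body text and Sensitivity Analysis 1 follows its own row, the two can also differ because of this rating, which has nothing to do with the question being tested.

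For confirmed BOR, the categories should be exclusive. The unconfirmed rule makes them so for this rating and the confirmed rule does not.

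**Working it through.** **Plan's own figure.** The documents give no figure for the effect of PFS censoring. The design figure reproduces: with 141 participants and success at 22 responses, the exact one-sided alpha is 2.39% and the power at 18% is 80.07%, against the stated 80%. It plays no part below, because Non-CR/Non-PD is not an objective response.

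**1. Does a Non-CR/Non-PD scan count for censoring?**

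| Place in SAP 14.4 | Test applied to the scan | Counts? |
|---|---|---|
| Summary table, primary row | progression-free | yes |
| Body text | available and evaluable | yes |
| Table 5 footnote, primary column | CR, PR or SD | no |
| Summary table and Table 5, Sensitivity Analysis 1 | CR, PR or SD | no |
| Sensitivity Analysis 2 | CR, PR or SD, Investigator reads | rating cannot occur |

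**2. Censoring time for one participant.** SAP 14.4 formula: PFS = (censoring date − first dose date + 1)/30.4375 months. Take a participant with no event, all scans Non-CR/Non-PD, the last at week 40 (day 280 after first dose).
- Primary row or body text: (280 + 1)/30.4375 = 9.23 months.
- Footnote, or Sensitivity Analysis 1: (0 + 1)/30.4375 = 0.03 months.
- With the last scan at week 16 or 24, the first figure is 3.71 or 5.55 months; the second stays at 0.03.

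**3. Effect on the 6-month PFS rate.** Assumptions, none from the documents: k of 141 participants have the rating and are event-free at 6 months, the others have a 25% rate, and nobody else is censored before 6 months. If the k participants are kept, the rate is ((141 − k) × 0.25 + k)/141. If they are censored on Day 1, it is 25%.
- k = 1: 36/141 = 25.53%, a difference of 0.53 points.
- k = 2: 36.75/141 = 26.06%, 1.06 points.
- k = 3: 37.5/141 = 26.60%, 1.60 points.

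A Kaplan-Meier illustration with exponential PFS (assumed medians of 1.8, 2.5 and 4.0 months in the others) agrees: 0.5 to 0.6 points for k = 1 and 1.4 to 1.9 for k = 3. The median does not move for k = 1, and moves by less than 0.1 months for k = 3.

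**4. Confirmed BOR.** Take Non-CR/Non-PD at week 8 and PD at week 16, with no measurable disease.
- Non-CR/Non-PD rule: week 8 is at or after week 6, before progression, and not CR. Met.
- Confirmed PD rule: week 16 is within 16 weeks, and the participant does not qualify for CR, PR or SD. Also met.
- Unconfirmed PD rule: the participant already meets Non-CR/Non-PD, so PD is excluded. One category only.

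**The case against.** **The footnote is only a note to a summary.** SAP 14.4 says that Table 5 also summarizes the censoring rules, and the fuller text and the protocol would keep the scan. This stands as far as it goes. A reader might infer from the footnote that primary PFS accepts only CR, PR or SD scans and that IRC PFS is therefore biased low. The documents do not support that: for the primary analysis there are competing rules, and a downward effect needs the footnote to prevail and such participants to exist. But the SAP gives no order of precedence, and Sensitivity Analysis 1 has no alternative wording to fall back on.

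**The case is designed out.** The IRC verifies measurable disease before enrollment and eligibility waivers are not permitted. This is why the point is small. It does not remove it, since the SAP itself allows for a disagreement at the efficacy read and gives the rating its own category.

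**Few participants could be touched.** Correct. A countable PD or death is an event under every version, and Investigator reads cannot carry the rating. PFS is descriptive.

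**A best response is one category by nature, and the unconfirmed rule shows the intent.** True, which makes the confirmed-BOR gap easy to close. As written, though, the rule does not say which category wins.

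**Disease control rate.** A reader might also infer that DCR is wrong to omit the rating. SAP 14.1 says: "Disease Control Rate (DCR) is defined as the proportion of participants with BOR according to evaluation criteria of CR, PR, or SD". That is an explicit definition, Non-CR/Non-PD is tabulated separately, and DCR is not among the listed primary or secondary endpoints in the text available. It is a matter of choice, and no change is asked for.

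**Conclusion.** Two wording defects hold, both conditional on an IRC rating that the SAP provides for but does not expect. For primary IRC PFS the SAP contradicts itself, and in Sensitivity Analysis 1 the only stated rule discards progression-free scans. The censoring date of an affected participant can move from 9.23 to 0.03 months in the week-40 example. At trial level this is about 0.5 points on the 6-month PFS rate per affected participant. That figure assumes the participant is event-free at 6 months and a 25% rate in the others; the number affected is unknown and may be zero. Separately, one sequence of scans satisfies two confirmed-BOR categories. The confirmed ORR test, its power and Investigator-assessed PFS do not change. The point is minor and worth correcting because the correction is so cheap.

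**What to change.** 1. In the Table 5 footnote and the Sensitivity Analysis 1 row of the SAP 14.4 summary table, replace the list CR, PR or SD with CR, PR, SD or Non-CR/Non-PD, so that both agree with the primary row and the body text.
2. In the confirmed-BOR definition of PD in SAP 14.1, add Non-CR/Non-PD to the excluded categories, as the unconfirmed definition already does.

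The cost is a few words in the SAP and the matching lines of the derivation specification. No new data, no protocol amendment and no change to sample size are needed.

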#### 14.4.1 Sensitivity analysis for PFS

The two following sensitivity analyses will be conducted:

1. PFS counting all events (PD and death) regardless of the start of a new anticancer therapy and ignoring the number of missing evaluable tumor assessments before progression or death
2. PFS as assessed by the Investigator (described above in Section 14.4)

Those sensitive analyses will be supported with Kaplan-Meir plots. Listing of progression-free survival by the Investigator will also be provided.

#### 14.4.2 Subgroup analysis for PFS

PFS according to RECIST 1.1 as adjudicated by IRC will also be evaluated on all subgroups as defined in Section 8.2. This will be repeated for Japanese participants including only the ADA and nAb status subgroup.

For the ADA and nAb subgroups, participant listings will provide the following information: participant ID, age, sex, race, ADA status, nAb PD-L1 assay status, nAb TGF- $\beta$  assay status, date of first administration, date of last tumor assessment, date of event/censoring, event/censoring reason, time to event. Two listings will be created: for the ADA positive participants and for nAb positive in either assay (PD-L1 and TGF- $\beta$ ) participants.

Participants with missing subgroup category will not be included in the related subgroup analysis. Those subgroups analyses will be supported by Kaplan-Meir and forest plots (based on PFS rates at 6-month and 12-month).

### 14.5 Duration of Response (Secondary Endpoint)

Analysis (Analysis Population)	Derivation	Statistical Analysis Methods	Missing data handling
Secondary endpoint: Duration of Response (DOR)			
Secondary analysis (ITT)	The duration of overall response is measured from the time from first documentation of confirmed objective response (CR or PR) to the date of first documentation of objective progression of disease (PD) or death due to any cause, whichever occurs first. This definition applies only to participants who experienced confirmed objective response. It will be measured according to RECIST 1.1 as measured by the IRC and the Investigator	Kaplan-Meier estimates (product-limit estimates) will be presented together with a summary of associated statistics (median time, 3-, 6-, 9-, 12-, 24-month rate estimates) including the corresponding two-sided 95% confidence intervals. The confidence intervals for the median will be calculated according to Brookmeyer and Crowley (1982) and confidence intervals for the survival function estimates at above defined timepoints will be derived using the log-log transformation according to Kalbfleisch and Prentice (2011) (conftype=loglog default option in SAS Proc LIFETEST). The estimate of the standard error will be computed using Greenwood's formula.	Same censoring rules as for PFS.

**Duration of response (DOR)** is defined for participants with a confirmed objective response, as the time from first documentation of confirmed objective response (CR or PR) to the date of first documentation of objective progression of disease (PD) or death due to any cause whichever occurs first:

DOR = (date of PD or death or censoring – date of confirmed objective response + 1)/30.4375 (months).

The censoring rules for DOR are as described above for PFS (primary definition in [Table 5](#)) in Section [14.4](#).

DOR of confirmed CR/PR according to RECIST 1.1 as measured by the IRC and the Investigator will be described. Considering confirmed CR/PR involve having at least two objective responses, the date of occurrence of the first CR/PR will be used as date of objective response.

The analysis of DOR will be performed with a Kaplan-Meier method (product-limit estimates) and a summary of associated statistics will be presented including corresponding two-sided 95% CIs. The CIs for the median will be calculated according to Brookmeyer and Crowley (1982) and CIs for the survival function estimates will be derived using the log-log transformation according to Kalbfleisch and Prentice (1980) (CONFTYPE=loglog default option in SAS PROC LIFETEST). The estimate of standard error will be computed using Greenwood's formula.

DOR rates with their CI at 3, 6, 9, 12 and 24 months will be presented, as well as the number of participants at risk and failed.

The time to and duration of response per participant having a confirmed objective response (including delayed response, see Section [14.7](#) below) will be displayed in swimmer graphs. Kaplan-Meier figures will also be provided.

Listings will be provided with the following information: participant identifier, age, sex, race, date of first study treatment administration, date of first response, date of last tumor assessment, censored (Y/N), date of event/censoring, event/censoring reason and duration of response.

